44 • Z_α corresponds to the value of statistical confidence, which was pre-set at a 95% confidence level,
 45 for a type I error of 5% expressed as a two-tailed α value of 0.05. For this confidence level, the Z
 46 value was 1.96.

- 1 • $Z\beta$ represents the statistical power and was pre-set at the $Z_{1-\beta}$ value of 80% for a type II error of
2 20%, which corresponds to a β value of 0.20. For this statistical power, the standardized Z score was
3 0.842.
- 4 • σ is the standard deviation of waist circumference (WC), insulin sensitivity, and insulin secretion in
5 patients with MetS.
- 6 • δ is the expected difference in waist circumference, insulin sensitivity, and insulin secretion in
7 patients with MetS.

8 A total of 28 patients, 14 for each study group, was the result obtained with the highest number of required
9 patients, including an additional 20% to anticipate possible loss to follow-up.

10 **Criteria**

11 Inclusion criteria

- 12 • Age between 30 and 60 years
- 13 • Diagnosis of metabolic syndrome (MetS) according to the IDF criteria:
 - 14 ○ Waist circumference (WC) \geq 80 cm in women or \geq 90 cm in men, plus two or more of the
15 following elements:
 - 16 ▪ Systolic blood pressure (SBP) \geq 130 mmHg and/or diastolic blood pressure (DBP) \geq
17 85 mmHg
 - 18 ▪ Triglycerides (TG) \geq 150 mg/dL
 - 19 ▪ HDL cholesterol (C-HDL) $<$ 40 mg/dL in men or $<$ 50 mg/dL in women
 - 20 ▪ Fasting plasma glucose (FPG) \geq 100 mg/dL
 - 21 • BMI between 25.0 and 34.9 kg/m²
 - 22 • No pharmacological treatment for the components of MetS
 - 23 • Stable weight during the last three months (weight variation less than 10%)
 - 24 • Female participants declared the use of a contraceptive method to prevent pregnancy during the study
25 period
 - 26 • Signed written informed consent form

27 Exclusion criteria

- 28 • Women who are pregnant or breastfeeding
- 29 • History of kidney, thyroid, or liver disease
- 30 • Consumption of medications or supplements with proven properties that modify the behavior of
31 metabolic syndrome
- 32 • Glucose \geq 126 mg/dL or diagnosis of type 2 diabetes mellitus
- 33 • Total cholesterol (TC) $>$ 240 mg/dL
- 34 • Triglycerides (TG) $>$ 500 mg/dL

35 Elimination criteria

- 36 • Non-compliance of medication intake exceeding 20%
- 37 • Intolerance to any of the intervention ingredients
- 38 • Meeting an exclusion criterion during the study
- 39 • Experiencing a serious adverse event
- 40 • Withdrawal of consent

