43 **Outcome measures**

44 *Primary outcome measures*

- 45 • WC
- 46 • DBP
- 47 • SBP
- 48 • TG
- 49 • HDL-c
- 50 • Glucose
- 51 • Insulin sensitivity

- First-phase insulin secretion
- Total insulin secretion

Secondary outcome measures

- Body weight
- BMI (Body Mass Index)
- Body fat percentage
- Lipid profile (Total cholesterol, LDL-c, VLDL)
- Post-load glucose
- Insulin levels
- Liver enzymes (ALT, AST)
- Creatinine levels
- Adverse events

Measurement and evaluation procedures

Demographic determinations

- Age: Expressed in completed years at the start of the intervention.
- Sex: Referring to the phenotypic sex at birth, it was recorded as male or female.

Clinical determinations

- *WC*: It will be measured using a flexible measuring tape with the subject standing. The tape was placed parallel to the ground and without clothing at the measurement level. The tape was positioned at the midpoint between the costal margin and the iliac crests at the end of a normal exhalation.
- *Weight*: It will be measured with the participant standing in a bipedal position, wearing light clothing, without shoes, and with an empty bladder prior to measurement. A stationary bioelectrical impedance scale will be used.
- *BMI*: It will be obtained by calculating the ratio of body weight in kg to the square of height in meters.
- *Body Fat*: It was determined using scale that utilizes the bioelectrical impedance method. Through a low-frequency signal, it calculates body fat and body composition.
- *SBP/DBP* (Systolic Blood Pressure/Diastolic Blood Pressure): It was determined using a digital sphygmomanometer. The participant was in a seated position after at least 5 minutes of rest. The cuff will be placed 3 cm above the elbow fold of the left arm. Two measurements will be taken to obtain the average blood pressure.

Clinical laboratory procedures

Oral Glucose Tolerance Test (OGTT)

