To perform this test, each patient will be administered an oral solution containing 75 g of anhydrous dextrose in 300 mL of water after fasting. By temporarily placing a peripheral venous catheter, 5 mL of blood will be drawn into a sterile dry tube at 0, 30, 60, 90, and 120 minutes after the administration of dextrose. The sample extraction procedure will be performed using sterile and disposable materials. The sample will be allowed to clot at room temperature, and then centrifuged at 3500 rpm for 15 minutes. The supernatant serum will be collected for subsequent clinical chemical analysis.

Laboratory determinations

The laboratory determinations will be performed using simple enzymatic-colorimetric techniques. For this purpose, the Erba Mannheim® XL100 automated clinical chemistry analyzer will be used, operated by a single chemist assigned to this study. The equipment will be routinely calibrated according to the laboratory logbook.

- *Glucose*: Glucose Oxidase/Peroxidase Method. The glucose present in the sample reacts with glucose oxidase, producing hydrogen peroxide, which then condenses with aminoantipyrine and phenol in the presence of peroxidase, forming the quinonimine chromogen. The chromogen is quantified in

proportion to the glucose concentration (COD 11538 Reagent, Biosystems S.A.). (Intra-assay coefficient of variation [CVa] = 0.6%, inter-assay coefficient of variation [CVe] = 0.8%)

- *TG*: Glycerol Phosphate Oxidase/Peroxidase Method. The triglycerides (TG) present in the sample are hydrolyzed by lipase, resulting in the formation of glycerol and fatty acids. In the presence of ATP and glycerol kinase, glycerol-3-phosphate is synthesized, which is then oxidized to dihydroxyacetone phosphate and hydrogen peroxide. The hydrogen peroxide, along with chlorophenol and aminoantipyrine, condenses in the presence of peroxidase, releasing the quinonimine chromogen. The complex is quantified in proportion to the triglyceride concentration (COD 11529 Reagent, Biosystems S.A.). CVa = 1.4%, CVe = 1.9%.

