- *Insulin*: For the determination of insulin, the enzyme-linked immunosorbent assay (ELISA) sandwich method was used. In this technique, samples and the conjugate reagent (biotinylated anti-insulin and HRP) are added to a streptavidin-coated surface. Insulin in the serum binds to the corresponding antigen pair, forming a sandwich complex, which immobilizes on the surface. After the addition of a substrate, a chromatic reaction occurs proportional to the insulin concentration. CVa = 3.1%, CVe = 4.5%.

40 Calculations

41 C-LDL and VLDL concentrations:²²

42 Formula de Friedewald: $C-LDL = CT - \left(C-HDL + \frac{TG}{5} \right)$ $VLDL = \frac{TG}{5}$

43 Glucose and insulin AUC: The calculation was performed using the mathematical formula proposed by
44 Tai..²³

45
$$\text{Area} = \frac{1}{2} \sum_{i=1}^n x_{i-1} (y_{i-1} + y_i)$$

46 Indices

47 Matsuda Index: It is used to calculate insulin sensitivity using the following formula:²⁴

48 Matsuda index =
$$\frac{10000}{\sqrt{(Gluc_0 * Ins_0) * (Gluc_{\text{mean } 0-120} * Ins_{\text{mean } 0-120})}}$$

Stumvoll Index: It is used to calculate the first-phase insulin secretion using the following formula.²⁵

$$\text{Stumvoll index} = 1,283 + 1.829 \times \text{Ins}_{30} - 138.7 \times \text{Gluc}_0 + 3.772 \times \text{Ins}_0$$

Total insulin secretion: It is used to calculate the first-phase insulin secretion using the following formula.²⁶

$$\text{Total insulin secretion} = \frac{\text{AUC Insulin}_{0-120}}{\text{AUC Glucose}_{0-120}}$$

Other determinations

Adherencia al tratamiento

Each participant will be given an adherence and monitoring diary in which they will be asked to record each intake of the intervention capsules. This diary is designed to record the date and time of each intake for a period of 12 weeks.

During each visit throughout the intervention, the patient will be asked to return the assigned intervention bottle containing any capsules that have not been taken, in order to calculate and estimate the adherence percentage.

Adverse events

The patient will record in the adherence and monitoring diary any symptoms or adverse changes in their health status during the medication intake period. A direct contact telephone number with the investigators will be provided to consult and report any unforeseen events.

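### Does the Stumvoll index need a change to the plan because its formula is printed without units?

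*Combined protocol and SAP*

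**What the plan says.** Under *Primary outcome measures* the plan lists nine variables, among them "First-phase insulin secretion". Fasting glucose is on the same list.

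The calculation is under *Indices*: "Stumvoll Index: It is used to calculate the first-phase insulin secretion using the following formula". The formula is 1,283 + 1.829 × Ins30 − 138.7 × Gluc0 + 3.772 × Ins0, with no unit for any term or for the result. The Matsuda index, introduced with "It is used to calculate insulin sensitivity using the following formula", uses the same fasting symbols, also without units.

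*Laboratory determinations* gives methods and coefficients of variation but no reporting units. The glucose entry describes a signal in "proportion to the glucose concentration (COD 11538 Reagent, Biosystems S.A"; the insulin entry says "a chromatic reaction occurs proportional to the insulin concentration. CVa = 3.1%, CVe = 4.5".

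For participants' glucose, a unit appears only in the eligibility criteria, in mg/dL: the 100 mg/dL metabolic syndrome component and the exclusion at "126 mg/dL or diagnosis of type 2 diabetes mellitus". Insulin carries a unit only in two background mouse studies, pg/mL in one and μU/mL in the other. No conversion is described.

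**The concern.** The Matsuda index is built from products and total secretion is a ratio of areas. A change of unit multiplies either by a constant, so patient ranks and group tests stay the same. The Stumvoll index adds terms with fixed coefficients, so a change of unit changes the weight of glucose against insulin. It is the only one of the three derived outcomes for which the unit affects the test result.

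A reader who takes the plan's only glucose unit at face value would enter mg/dL. The glucose term would then swamp the rest: a primary outcome meant to measure insulin secretion could become a near-copy of fasting glucose, another primary outcome, and a real change in 30-minute insulin could be lost. The plan's rank-based tests would not protect against this, because the ranks themselves change.

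**Working it through.** **Inputs.** The coefficients are from *Indices*; the 100 and 126 mg/dL values are from the eligibility criteria. Everything else is assumed, because the documents give no spreads or insulin values: 18 mg/dL per mmol/L; insulin × 6 from μU/mL to pmol/L and × 34.8 to pg/mL; SDs of 9 mg/dL (fasting glucose), 40 μU/mL (Ins30) and 6 μU/mL (Ins0); independent inputs. The plan prints no value for the index, so there is no figure of its own to reproduce.

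**One patient** (100 mg/dL, Ins30 80, Ins0 12 μU/mL):

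- Glucose in mg/dL: 1,283 + 146.3 − 13,870 + 45.3 = −12,395.
- Glucose in mmol/L (100/18 = 5.556): 1,283 + 146.3 − 770.6 + 45.3 = +704.
- Insulin in pmol/L: −11,437 and +1,662 respectively.

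**Ranking.** Take two patients, both with Ins0 8 μU/mL. A has glucose 95 mg/dL and Ins30 40; B has 105 and 120. In mg/dL, A is −11,790 and B −13,031, so A ranks higher. In mmol/L, A is +654 and B +724, so B ranks higher. The unit does matter for the test.

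**Share of variance from glucose.** The share is (138.7 × SDg)² / [(138.7 × SDg)² + (1.829 × SD30)² + (3.772 × SD0)²].

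- mg/dL with μU/mL: 1,558,253 / (1,558,253 + 5,352 + 512) = 99.6%.
- mmol/L with μU/mL (SDg 0.5): 4,809 / (4,809 + 5,352 + 512) = 45%.
- mg/dL with pg/mL: 1,558,253 / (1,558,253 + 6,481,953 + 620,304) = 18%.

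A true difference of one SD in Ins30 shows in the index as 1.829 × SD30 divided by the index SD. Power is for a two-sided t-test at 0.05 with 14 per group.

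| Insulin unit | Glucose mg/dL: share, effect, power | Glucose mmol/L: share, effect, power |
|---|---|---|
| μU/mL | 99.6%, 0.06 SD, 5% | 45%, 0.71 SD, 44% |
| pmol/L | 88%, 0.33 SD, 13% | 2%, 0.94 SD, 67% |
| pg/mL | 18%, 0.87 SD, 60% | 0.1%, 0.96 SD, 68% |

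**Sensitivity.** With a glucose SD of 5 to 12 mg/dL, the mg/dL shares are 98.8–99.8% (μU/mL), 69–93% (pmol/L) and 6–28% (pg/mL). A simulation with correlated insulin values (0.6 between the two insulins, 0 to 0.2 with glucose) gave R² with fasting glucose of 0.96–0.998, 0.28–0.94 and at most 0.33 in the same order.

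**Sign.** Over an assumed range (glucose 70–125 mg/dL, Ins30 20–300, Ins0 2–40 μU/mL), the index with glucose in mg/dL runs from −16,010 to −7,726; its top is −4,229 with insulin in pmol/L. With pg/mL it reaches about +15,900 at 70 mg/dL and the highest insulin values, so it is not negative throughout.

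**What the coefficients suggest.** The constant and the glucose term cancel at 1,283 / 138.7 = 9.25 glucose units. The exclusion limit of 126 mg/dL is 126/18 = 7.0 mmol/L, so eligible entry values lie below 9.25 in mmol/L and far above it in mg/dL. The printed formula itself warns an analyst that mg/dL does not fit.

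**The case for a change.** The strongest case for a change is that this is a primary outcome and the plan does not point clearly to the units. The Stumvoll formula cites reference 25, while the printed list ends at 22; a paper on estimating insulin release from the glucose tolerance test is item 20. Gluc0 appears in two adjacent formulas with no conversion between them. Stating the units would take two or three lines.

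Much of this stands. The units are missing, they affect the test, and a note of them would be good practice. The safeguard of seeing implausible values is also incomplete: an output near −12,000 gives itself away, but with glucose in mmol/L the index is positive in both μU/mL (+704) and pmol/L (+1,662), so its sign would not reveal a wrong insulin unit. Nor does sign settle the glucose unit by itself: in mmol/L the formula gives −199 at glucose 11, Ins30 20 and Ins0 2 μU/mL, although that glucose is outside the eligibility limit.

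What does not stand is the step from a missing unit to a wrong calculation. The mg/dL figures for participants are entry thresholds, not inputs assigned to this formula. The index is named and published, so its units are fixed by its definition and are not open to the analyst's choice. The wrong citation number is a clerical slip, since the list contains a matching paper. Two neighbouring points are also clerical: the AUC formula does not define its x term, which is the sampling interval if the sum is the trapezoidal rule, and the ratio of areas carries a description copied from the entry above it, "Total insulin secretion: It is used to calculate the first-phase insulin secretion using the following formula".

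**Conclusion.** No change to the plan follows. The formula lacks units, but the plan states no wrong rule or number, and an analyst using a named index would take its units from its definition. If glucose were entered in mg/dL by mistake with insulin in μU/mL, the damage would be large: 99.6% of the variance from fasting glucose and power of about 5% instead of 44%. The planned means and SDs would then expose it, with values around −12,000. With pmol/L, glucose would still dominate under most assumed spreads; with pg/mL, one of the two insulin units in the documents, it would carry about 18%. A general claim that the outcome is strongly negative and mostly repeats fasting glucose therefore goes too far.

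These sizes rest on assumed SDs, independent inputs and a pure one-SD difference in 30-minute insulin. Power is from a t-test, whereas the only between-group test the plan names for quantitative variables is Mann-Whitney, and it uses all 14 per group, a number that already includes the 20% allowance for losses. The exact sizes could shift, but the conclusion does not depend on them: this is a gap in reporting detail that analysts fill sensibly.

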 5 • Determine and compare TG concentration before and after the intervention with fucoxanthin and
 6 placebo.
 7 • Determine and compare HDL-c concentration before and after the intervention with fucoxanthin and
 8 placebo.
 9 • Determine and compare fasting serum glucose level before and after the intervention with
 10 fucoxanthin and placebo.
 11 • Determine and compare insulin sensitivity before and after the intervention with fucoxanthin and
 12 placebo.
 13 • Determine and compare the total secretion of insulin before and after the intervention with
 14 fucoxanthin and placebo.
 15 • Determine and compare the first phase of insulin secretion before and after the intervention with
 16 fucoxanthin and placebo.

17 **Secondary objectives**

18 • Determine and compare body weight before and after the intervention with fucoxanthin and placebo.
 19 • Determine and compare BMI before and after the intervention with fucoxanthin and placebo.
 20 • Determine and compare body fat percentage before and after the intervention with fucoxanthin and
 21 placebo.
 22 • Determine and compare insulin concentration before and after the intervention with fucoxanthin and
 23 placebo.
 24 • Determine and compare post-load glucose concentration after oral administration of 75 g of glucose
 25 before and after the intervention with fucoxanthin and placebo.
 26 • Determine and compare total cholesterol (TC), LDL cholesterol (LDL-c), and VLDL before and after
 27 the intervention with fucoxanthin and placebo.
 28 • Determine and compare AST and ALT levels before and after the intervention with fucoxanthin and
 29 placebo.
 30 • Determine and compare creatinine and uric acid levels before and after the intervention with
 31 fucoxanthin and placebo.
 32 • Describe the tolerability of treatment with fucoxanthin and placebo.

34 **MATERIALS AND METHODS**

35 **Design**

36 Randomized, double-blind, and placebo controlled clinical trial.

37 **Universe**

38 Men and women aged 30 to 60 with a diagnosis of MeS, residing in the metropolitan area of Guadalajara.

39 **Sample**

40 The sample size was calculated using a formula for the difference in means in clinical trials. A confidence
 41 level of 95%, a power of 80%, the standard deviation, and the expected difference obtained from the response
 42 variables in patients with metabolic syndrome were considered.

$$43 n = 2 \left(\frac{(Z_\alpha - Z_{1-\beta})(\sigma)}{\delta} \right)^2$$

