During each visit throughout the intervention, the patient will be interviewed and physically examined, if necessary, in search of changes in health status that may be related to the consumption of the formulation's ingredients.

Grupos de estudio y administración de la intervención

Two groups of 14 patients each will be formed:

- Fucoxanthin: Each patient will receive a capsule containing 12 mg of fucoxanthin every 24 hours. They will ask to take one capsule with the first bite of breakfast for a duration of 12 weeks.
- Placebo: Each patient will receive a placebo capsule (Magnesium stearate) that is indistinguishable from fucoxanthin. They will be instructed to take one capsule with the first bite of breakfast for a duration of 12 weeks.

Allocation of intervention and blinding

The treatment assignment will be performed through simple randomization, using the method of a simple random number table. By using computer software, each intervention will be randomly assigned an identification with a numerical code corresponding to an identified intervention within Group A or Group B. The patient and the researcher will not be informed of which pharmacological intervention corresponds to each numerical code.

DATA COLLECTION AND STATISTICAL ANÁLISIS PLAN

All the results will be collected in a digital database designed for this study, where no confidential personal information not related to the study variables will be recorded. The information entered in the database will be transferred for analysis in the statistical software IBM SPSS Statistics® for Windows®. The statistical analysis will be conducted at the end of the total data collection once the intervention in the included patients has finished. All patients will be included in the intention-to-treat analysis. In descriptive statistics, measures of central tendency and dispersion will be used. Quantitative variables will be presented with means and standard deviations. Qualitative variables will be presented with frequencies and percentages.

The Shapiro-Wilk test will be performed to determine the normality of the sample distribution in each variable. If the sample distribution is found to be abnormal, non-parametric tests will be used. The analysis between groups (independent samples) will be analyzed using the Mann-Whitney U test for quantitative variables, and the X² test or Fisher's exact test for qualitative variables. Intragroup analysis (two related

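### Visit questioning about adverse events is limited to possibly related changes while the diary and telephone line are not, and no event follow-up is specified after a participant stops

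*Combined protocol and SAP*

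**What the plan says.** All references are to the combined protocol and SAP. Other determinations, Adverse events, sets up three routes for reporting events.

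- **Diary.** The patient writes down "any symptoms or adverse changes in their health status during the medication intake period". The same diary also serves adherence: "This diary is designed to record the date and time of each intake for a period of 12 weeks".
- **Telephone.** The patient receives a number on which "to consult and report any unforeseen events". No end date is given.
- **Visits.** "During each visit throughout the intervention, the patient will be interviewed and physically examined, if necessary", and this is done "in search of changes in health status that may be related to the consumption of the" formulation's ingredients.

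Adverse events are listed under Secondary outcome measures. The matching item under Secondary objectives is "Describe the tolerability of treatment with fucoxanthin and placebo". AST, ALT and creatinine are also measured in both groups.

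Elimination criteria include "Intolerance to any of the intervention ingredients" and "Experiencing a serious adverse event". The section does not say what is recorded about such a participant afterwards.

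The analysis plan gives frequencies and percentages for qualitative variables, with a chi-squared or Fisher test between groups. It names no analysis specific to adverse events.

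**The concern.** Two things in this section weaken the adverse-event data.

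First, the sources use different definitions. The diary and the telephone line have no causality condition. The visit interview, the only source in which a clinician asks the questions, looks for changes already thought possibly related. That places a causality opinion ahead of elicitation. The opinion has little to rest on: the Rationale calls human research limited and says more is needed to establish safety, and the Background gives no adverse-event profile from the human studies it cites. An effect that nobody suspects is the one this wording is least likely to bring out.

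Second, collection is described only up to the end of treatment. Participants who stop for intolerance or a serious event say most about tolerability, yet the plan specifies no later contact with them and no recording of how the event ended.

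What is at stake is the completeness of one secondary outcome in a small trial. The primary outcomes are not affected.

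**Working it through.** No figure in the plan decides this point, so the main check sets the sections side by side.

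| Source | Which events | Time window | Who starts it |
|---|---|---|---|
| Diary | Any symptom or adverse change | Intake period | Patient |
| Telephone | Any unforeseen event | None stated | Patient |
| Visit interview, examination if needed | Possibly related changes | Visits during the intervention | Investigator |
| AST, ALT, creatinine | All values, whatever the cause | Before and after | Scheduled |

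Four things follow.

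1. The causality condition appears in one row only.
2. That row is the only one in which someone other than the patient asks about symptoms. The two unrestricted symptom sources depend on the patient volunteering the event.
3. Nothing says how the rows are merged, or what happens when a diary entry is thought unrelated at the visit.
4. The diary and visits are tied to treatment. The telephone line could be used later, but no contact is scheduled. The sections on adverse events and elimination specify no recording of event outcome, severity, seriousness or causality.

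**Scale at 14 per group.** The group size comes from the Sample section. The event rates and counts below are assumptions, because the documents give none.

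- Chance of at least one affected patient in an arm, 1 − (1 − p)^14: 51% for p = 5%, 77% for p = 10%, 96% for p = 20%.
- One-sided 95% upper bound on the true risk when 0 of 14 are affected, 1 − 0.05^(1/14): 0.193, or about 19%.
- Two-sided Fisher exact p: 0.041 for 0/14 versus 5/14, and 0.098 for 0/14 versus 4/14.

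The last line shows that one affected patient can move a comparison across the plan's 0.05 threshold. These results show how sensitive a table of this size is. They do not estimate how many events the visit wording would miss.

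**The case against.** The strongest reply is that the visit wording does little harm because other sources cover the gap. The diary and telephone line take events whatever their cause, and the liver and creatinine tests are run regardless. A possible relation is also a low bar, and it is applied by staff who do not know the allocation. The objective is to describe tolerability, whereas most other secondary objectives are to determine and compare.

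Much of this stands, and it rules out several stronger readings that a reader might infer:

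- *That the tolerability data as a whole are filtered by causality.* Only the visit source carries the condition.
- *That events judged unrelated are thrown away.* The text says what the interview looks for. It contains no rule excluding what is found or reported.
- *That all recording stops with the last capsule.* This fits the diary wording, but the telephone line has no stated end.
- *That an event ending treatment cannot be captured.* It begins during intake, so the diary, the telephone line or the reason for elimination can record it. What is unspecified is its follow-up.
- *That the arms are biased against each other.* Blinded staff ask the same question in both arms. An unexpected drug effect that went unelicited would be lost from the active arm, but whether that happens depends on what the other sources capture, which the documents do not show.

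The reply does not remove two facts. The other symptom sources are patient-initiated, so they do not replace an open question from an investigator. And none of the sources comes with a follow-up rule after stopping.

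**Conclusion.** The point holds in a limited form. The visit wording is narrower than the diary and telephone wording, the documents do not reconcile them, and follow-up of events after stopping or elimination is not specified. The likely consequence is under-elicitation of unexpected events at the one investigator-led source, together with incomplete information on events that end treatment.

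The size cannot be stated. It depends on true event rates and on the share of events that reach the diary or telephone line, and the documents give neither. If patients report everything, the loss from the visit wording could be close to nil.

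The conclusion assumes that the visit wording is applied as written. It also assumes that the removed title and consent pages contain no follow-up rule, which cannot be checked here.

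The change is worth making because it is cheap and because the protocol itself treats safety as an open question.

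**What to change.** Four changes to wording and the case report form:

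1. In Adverse events, replace the restricted visit phrase with: *in search of any change in health status since the last visit, whatever the suspected cause*.
2. Pool diary, telephone and visit reports into one all-cause event list. Record the blinded causality opinion as a separate field, so that it does not decide whether an event is listed.
3. In the analysis plan, state that all events are described by arm.
4. Add one telephone contact after the last dose, including for participants who stop early or are eliminated, and record the outcome of any event still open.

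The cost is more minor events to record and one call for each of 28 patients. A telephone line for participants is already planned. No dose, treatment schedule or elimination criterion changes.

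### The plan states two groups of 14, but the simple randomisation it names does not fix group sizes: 28 independent 1:1 assignments give 14:14 only 14.9% of the time

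*Combined protocol and SAP*

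**What the plan says.** The group sizes appear twice in the combined protocol and SAP. Under Materials and Methods, Sample: "A total of 28 patients, 14 for each study group", a figure described as "including an additional 20% to anticipate possible loss to follow-up". Under the heading on study groups and administration of the intervention (printed in Spanish): "Two groups of 14 patients each will be formed".

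The method comes in the next section, Allocation of intervention and blinding: "The treatment assignment will be performed through simple randomization", "using the method of a simple random number table". It goes on to say that, by software, "each intervention will be randomly assigned an identification with a numerical code corresponding to an identified intervention within Group A or Group B". It does not say how many codes belong to Group A and how many to Group B. No section mentions blocks, a fixed-total list, stratification or any other restriction.

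Two further statements bear on the size of the effect. The statistical analysis plan says "All patients will be included in the intention-to-treat analysis", and for data that are not normal the between-group comparison "will be analyzed using the Mann-Whitney U test".

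**The concern.** In its ordinary sense, simple randomisation means that each patient is assigned independently, as by a coin toss. That method fixes the chance of each assignment, not the arm totals. Two groups of exactly 14 are therefore not a property of the method named. Either the method or the group sizes are described wrongly, or 14 is only an expected size and the text does not say so.

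What is at stake is efficiency and reproducibility. In a trial of 28, chance imbalance can leave one arm noticeably small before any patient is lost, and a restricted list avoids this at almost no cost. A reader also cannot tell from the text how the list is to be built.

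**Working it through.** **Inputs from the plan.** Total 28, with 14 per group; two-sided alpha 0.05 (Z = 1.96); power 80% (Z = 0.842); 20% allowance for loss, already inside the 14. The SD and the expected difference are defined but given no values.

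**The plan's own figure.** The 28 cannot be reproduced without an SD and a difference. Only the allowance can be checked: 11 evaluable per arm gives 11 × 1.2 = 13.2 or 11 / 0.8 = 13.75, and both round up to 14.

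**Split probabilities.** Assume 28 independent assignments with probability 0.5, and let X be the number in one arm, X ~ Bin(28, 0.5).

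- P(X = 14) = C(28,14) / 2^28 = 40,116,600 / 268,435,456 = 0.149, so the arms are unequal 85.1% of the time.
- P(12 ≤ X ≤ 16) = 175,844,430 / 268,435,456 = 0.655.
- P(smaller arm ≤ 10) = 2 × P(X ≤ 10) = 49,642,666 / 268,435,456 = 0.185.

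**Information.** Relative to 14:14, a split x:(28 − x) keeps 4x(28 − x)/28². This is 0.980 at 12:16 and 0.918 at 10:18, the latter equal to 28 × 0.918 = 25.7 patients split evenly. The mean over all splits is 1 − 1/28 = 0.964.

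**Power (illustration).** I assume that 80% power was targeted with n evaluable per arm before the allowance, so that the standardised difference is d = (1.96 + 0.842) × √(2/n). This takes the usual sum of the two Z values; the printed formula shows a minus sign between them. The range for n runs from 10.4 (10.4 / 0.8 = 13, so anything just above rounds up to 14) to 12 (12 × 1.2 = 14.4, which rounds to the nearest whole number as 14). Power is for a two-sided 5% t-test (noncentral t, 26 df) with all 28 analysed.

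| n assumed | d | Power at 14:14 | Average over splits | Power at 10:18 |
|---|---|---|---|---|
| 10.4 | 1.229 | 87.9% | 86.6% | 85.0% |
| 11 | 1.195 | 86.0% | 84.7% | 83.0% |
| 12 | 1.144 | 83.0% | 81.5% | 79.7% |

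From unrounded values, the average loss is 1.3 to 1.5 points and the loss at 10:18 is 2.8 to 3.3 points. Across the same range the loss is about 0.2 points at 13:15 and 0.7 to 0.8 at 12:16.

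**Cross-check with another anchor.** If power is instead taken as 80% at 14:14 (normal approximation), it is 79.2% at 12:16 and 76.6% at 10:18. These losses, 0.8 and 3.4 points, are of the same order.

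**The case against.** The strongest reply is that the conflict depends on one reading. A random number table can just as well be used to draw 14 of 28 numbers, and the sentence on numerical codes would fit a prepared set of coded treatments. In a translated text, 'simple' may mean no more than unstratified. The plan states the fixed sizes immediately before it names the method. This stands in part: the 14.9% describes the literal reading only, and the documents do not establish that the sizes were really left to chance. They do not describe a fixed-total draw either, so the text needs correcting on both readings.

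The second reply is that the effect is slight. This is right. Simple randomisation is a valid method, about two thirds of splits cost less than one power point, and the 20% allowance means that the evaluable arms may differ under any list. In most of the illustrated range even 10:18 stays above 80% power; at the unfavourable end it is 79.7%.

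A reader might also infer more than the documents support:

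- That the comparison is biased or the sample size invalid. Unequal arms from independent assignment do neither.
- That a 10:18 split costs at least 3 power points. The loss depends on an assumed effect size and can be 2.8.
- That the Mann-Whitney test suffers more. Part of any apparent drop there comes from the discreteness of the statistic, so it does not measure the cost of imbalance.
- That only an exact 14:14 will do. A 13:15 split costs about 0.2 points.

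**Conclusion.** The point holds as a minor one. Under the ordinary meaning of simple randomisation, the plan states group sizes that its method does not deliver, and no section supplies a restriction that would. The probabilities of 14.9%, 65.5% and 18.5% are exact, given 28 independent 1:1 assignments. The power figures are illustrative: they rest on an assumed 10.4 to 12 evaluable per arm at 80% power, normal data with a t-test, and all 28 analysed. On that basis the avoidable loss is about 1.3 to 1.5 points on average and about 3 points at 10:18. The case for acting is that restriction costs almost nothing, not that the trial is at risk.

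**What to change.** In Allocation of intervention and blinding, replace simple randomisation with a computer-generated, concealed list that restricts the totals. Either of these is adequate:

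- A random permutation of 14 fucoxanthin and 14 placebo codes, assigned in sequence. This gives 14:14 with certainty.
- Permuted blocks. Seven blocks of 4 (7 × 4 = 28) give exactly 14:14. Randomly varying blocks, cut at patient 28, end at 14:14 or 13:15 and never worse: 14:14 occurs 81.1% of the time with equally likely sizes 2, 4 and 6, and 77.3% with sizes 4 and 6.

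If the numerical codes were already a fixed set of 14 and 14, correct the word 'simple' and state the 14 and 14. If independent assignment is deliberately kept, say that 14 per group is an expected size.

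The cost is one sentence and a different software setting. The small downside is that the last assignments in a block or a fixed list are slightly more predictable, which the indistinguishable coded capsules limit.
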